1.3.2. Preliminary Unpublished Data (blinded)

Subject Disposition and Baseline Characteristics (data-cutoff May 19, 2015)

Thirty-six subjects have been randomized, of which 12 have completed the study. To date, three subjects have discontinued from the study. One subject in Cohort 4 was no longer willing to participate and discontinued on Day 8; this subject was replaced with another subject. Two other subjects were no longer willing to participate in the study and were terminated early (1 each in the 1.0 mg/kg cohort and the 3.0 mg/kg cohort) and were not replaced.

The baseline characteristics of the subjects randomized to date in the SAD study are summarized in Table 1 below.

Table 1. Baseline Characteristics – SAD Cohorts, Study B3501001

Characteristics	Placebo N=9	Cohort 1 (0.3 mg/kg) N=6	Cohort 2 (1.0 mg/kg) N=6	Cohort 3 (3.0 mg/kg) N=6	Cohort 4 (6.0 mg/kg) N=9
Age ^{1,2}	57.1 ± 6.5	60.7 ± 4.5	60.7 ± 6.2	57.7 ± 4.5	57.4 ± 8.7
Gender ² (M:F)	4:5	5:1	2:4	3:3	5:4
Weight ^{1,2} (kg)	89 ± 21	93 ± 9	77 ± 14	90 ± 11	88 ± 16
BMI ^{1,2} (kg/m ²)	31.0 ± 4.6	32.3 ± 3.7	29.1 ± 3.3	30.8 ± 3.2	32.1 ± 3.4
Duration T2DM ³ (years)	10.9	13.4	10.0	8.5	8.1
Baseline HbA1c ^{1,4} (%)	8.7 ± 1.0	8.1 ± 0.9	7.7 ± 0.6	8.2 ± 0.5	8.3 ± 0.7

¹ Mean ± SD; Source; ² Table 14.1.2.1 (B3501001 IND Tables); ³ Table 14.1.2.2 (B3501001 IND Tables);

⁴ Table 14.4.7.5.1 (B3501001 IND Tables).

Pharmacokinetics (data-cutoff May 19, 2015)

As of May 19th 2015, preliminary, unpublished PK of PF-06293620 are available from the first 4 cohorts (0.3, 1, 3, and 6 mg/kg) in the ongoing single ascending dose study in subjects with T2DM. Following administration of single subcutaneous doses of PF-06293620, absorption was slow with median C_{max} occurring approximately 4-10 days post dose. After that the decline in concentration was slow and multiphasic with mean terminal half-life (t_{1/2}) ranging from 9 to 18 days as the doses increased from 0.3 to 3 mg/kg. Both C_{max} and total

exposure (AUC_{inf}) increased slightly greater than dose proportionally with increasing doses up to 6 mg/kg. Table 2 below summarizes the PF-06293620 preliminary, unpublished PK parameters.

Table 2. Geometric Mean (%CV) Plasma PF-06293620 Pharmacokinetic Parameter Values, Study B3501001 (Preliminary, unpublished, based on QCed data)

Parameter	PF-06293620 Treatment			
	0.3 mg/kg SC	1 mg/kg SC	3 mg/kg SC	6 mg/kg SC
N, n	6,2	6,5	6,6	6,0
AUC _{inf} (µg·hr/mL)	260	1748 (46)	6606 (45)	NC

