The proposed PF-06293620 doses in the MAD portion were selected based on the preliminary PK/PD analysis and simulation from available data from the first 4 cohorts in the ongoing SAD study. Fixed dosages of 75, 150 and 250 mg Q4W were selected for this study to allow for adequate characterization of both the dose-response relationship for glycemic analytes (FPG, MMTT, mean daily glucose [MDG] and HbA1C), as well as to identify the maximum tolerated dose. Modeling suggests minimal accumulation ($R_{ac}=1.14$) of PF-06293620 after 3 dosages at 75 mg Q4W and approximately 1.4 and 1.6-fold increase in the exposure is predicted at 150 and 250 mg Q4W dosages, respectively. However, the predicted exposure at the highest dose (250 mg Q4W, ~3.1 mg/kg) is not expected to exceed the observed exposure at 6 mg/kg single-dose. The 6 mg/kg dose was found to be safe and well-tolerated. Guided by the dose-response relationship for baseline-adjusted FPG, the doses of 75 mg, 150 mg and 250 mg Q4W are deemed appropriate and adequate to allow for characterization of the dose-response relationship for PK, and PD changes. The 250 mg dose is expected to result in maximal fasting plasma glucose lowering. The 75 mg Q4W would approximately represent the dose for 50% maximal effect (ED50) and an intermediate dose of 150 mg Q4W was also proposed.

Proposed MAD doses, along with anticipated safety margins are listed in Table 4 below. The predicted human C_{max} and AUC_{tau} at the highest proposed dose would be approximately 122- and 20-fold below, respectively, the maximum observed exposures at 200 mg/kg (SC) in monkey in the pivotal, 3-month, toxicity study.

Table 4. Proposed PF-06293620 MAD Doses and Predicted Safety Margins based on the Exposures in Monkeys

Proposed PF-06293620 MAD Doses (mg)	Regimen	Predicted PF-06293620 Human Exposure		Projected Safety Margin*(fold)	
		C_{max} (μ g/mL)	AUC_{tau} (μ g*hr/mL)	C_{max}	AUC
75	Q4W	3.0	1471	653	126
150	Q4W	8.0	4486	245	41
250	Q4W	16.1	9448	122	20
TBD	TBD	--	--	--	--

Exposure at NOAEL doses (200 mg/kg) in monkeys:

IV: $C_{max} = 12,100 \mu$ g/mL; $AUC = 625,000 \mu$ g*hr/mL

SC: $C_{max} = 1,960 \mu$ g/mL; $AUC = 185,000 \mu$ g*hr/mL

*Margin calculated based on the NOAEL exposure/predicted human exposure

Source: Supportive Table 6 (RN909 Study B3501001: Preliminary PK report, May 2015)

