2.2.2. Secondary Endpoints

- Single- and multiple-dose pharmacokinetic parameter estimates of PF-06293620 include: C_{max} , C_{av} , C_{min} , T_{max} , CL or CL/F , V_{ss} or V_z/F , half-life, AUC_{last} , AUC_{τ} , R_{ac} and AUC_{inf} as the data permit and as appropriate for SAD and MAD cohorts.

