9.3.1. Derivation of Pharmacokinetic Parameters

PK parameters following single and multiple-dose administration will be derived from the concentration-time profiles as appropriate as follows:

Single Dose PK Parameters

Parameter	Definition	Method of Determination
AUC _{last}	Area under the serum concentration-time profile from time zero to the time of the last quantifiable concentration (C _{last})	Linear/Log trapezoidal method
AUC _{inf} ^a	Area under the serum concentration-time profile from time zero extrapolated to infinite time	AUC _{last} + (C _{last} */k _{el}), where C _{last} * is the predicted serum concentration at the last quantifiable time point estimated from the log-linear regression analysis.
C _{max}	Maximum serum concentration	Observed directly from data
T _{max}	Time for C _{max}	Observed directly from data as time of first occurrence
t _{1/2} ^a	Terminal elimination half-life	Ln(2)/k _{el} , where k _{el} is the terminal phase rate constant calculated by a linear regression of the log-linear concentration-time curve. Only those data points judged to describe the terminal log-linear decline will be used in the regression.
CL/F ^{a,b}	Apparent clearance	Dose / AUC _{inf}
V _z /F ^{a,b}	Apparent volume of distribution	Dose / (AUC _{inf} * k _{el})
CL ^{a,c}	Clearance	Dose / AUC _{inf}
V _{ss} ^{a,c}	Steady-state volume of distribution	CL * MRT, where MRT is the mean residence time calculated as (AUMC _{inf} /AUC _{inf} - Infusion duration/2); AUMC _{inf} is area under the moment curve from time 0 extrapolated to infinity
AUC _{last(dn)}	Dose normalized AUC _{last}	AUC _{last} / Dose
AUC _{inf(dn)} ^a	Dose normalized AUC _{inf}	AUC _{inf} / Dose
C _{max(dn)}	Dose normalized C _{max}	C _{max} / Dose

^a If data permit

^b SC cohorts only

^c IV cohort only

Multiple Dose PK Parameters

Parameter	Day(s)	Definition	Method of Determination
AUC _τ	1, 57	Area under the concentration-time profile from time zero to time tau (τ), the dosing interval, where τ = 4 weeks (672 hours)	Linear/Log trapezoidal method
C _{max}	1, 57	Maximum serum concentration	Observed directly from data
C _{av}	1, 57	Average concentration	AUC _τ /τ
T _{max}	1, 57	Time for C _{max}	Observed directly from data as time of first occurrence
CL/F	1, 57	Apparent clearance	Dose / AUC _τ
C _{min}	57	Lowest concentration observed during the dosing interval	Observed directly from data

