t _{1/2} ^a	57	Terminal elimination half-life	Ln(2)/k _{el} , where k _{el} is the terminal phase rate constant calculated by a linear regression of the log-linear concentration-time curve. Only those data points judged to describe the terminal log-linear decline will be used in the regression.
V _z /F ^a	57	Apparent volume of distribution	Dose / (AUC _τ / k _{el})
R _{ac}	57	Observed accumulation ratio based on AUC	AUC _τ Day 57 / AUC _τ Day 1
R _{ac,Cmax}	57	Observed accumulation ratio based on C _{max}	C _{max} Day 57 / C _{max} Day 1
AUC _{τ(dn)}	1, 57	Dose normalized AUC _τ	AUC _τ / Dose
C _{max(dn)}	1, 57	Dose normalized C _{max}	C _{max} / Dose
C _{min(dn)}	57	Dose normalized C _{max}	C _{min} / Dose

^a If data permit

Note: Actual PK sampling times will be used in the derivation of PK parameters.

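### The multiple-dose Vz/F formula in Protocol 9.3.1 divides AUCtau by kel where it should multiply, so followed literally it does not give a volume

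*Protocol*

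**What the plan says.** Protocol 9.3.1 has two derivation tables, and both list Vz/F under the description "Apparent volume of distribution".

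- Single-dose table: "Dose / (AUC _{inf} * k _{el").
- Multiple-dose table, Day 57: "Dose / (AUC _τ / k _{el").

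The half-life row of the multiple-dose table obtains half-life as ln(2)/kel, where kel "is the terminal phase rate constant calculated by a linear regression of the log-linear concentration-time curve". In the same table CL/F is Dose divided by AUCtau, with AUCtau taken over the dosing interval, "where τ = 4 weeks (672 hours").

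Protocol 2.2.2 names the parameter among the single- and multiple-dose secondary endpoints: "CL or CL/F , V_{ss} or V_z/F , half-life".

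The SAP schedules multiple-dose Vz/F for Day 57 (Table 5) and lists its summary statistics (Table 8). SAP 8.3.1 says the parameters come from the serum concentrations by conventional noncompartmental methods. It gives no formula for Vz/F.

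**The concern.** The two tables give one parameter, under one description, two forms that cannot both be right. The change from AUCinf to AUCtau is not the problem: a multiple-dose table would be expected to use the AUC over the dosing interval, as the CL/F row does. The problem is the operator between AUC and kel.

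Section 9.3.1 is the only place in either document where the multiple-dose Vz/F derivation is written out. A programmer or a quality-control reviewer who checks output against the protocol would be checking against the wrong expression. At stake is the correctness of one descriptive secondary endpoint.

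**Working it through.** **Inputs**

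- Multiple-dose Vz/F as printed: Dose / (AUCtau / kel) (Protocol 9.3.1).
- Single-dose Vz/F: Dose / (AUCinf × kel) (Protocol 9.3.1).
- Multiple-dose CL/F: Dose / AUCtau, in volume per time (Protocol 9.3.1).
- kel: a rate constant, in 1/time, because half-life = ln(2)/kel (Protocol 9.3.1).
- For illustration only: predicted AUCtau at 150 mg every 4 weeks, 4486 µg·h/mL (Protocol 1.3.3, Table 4), and the preliminary single-dose half-life, "ranging from 9 to 18 days as the doses increased from 0.3 to 3 mg/kg" (Protocol 1.3.2).

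The text available for review gives no Vz/F value to reproduce, so the check is algebraic and dimensional.

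**Step 1: algebra**

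- Printed: Dose / (AUCtau / kel) = (Dose / AUCtau) × kel = (CL/F) × kel.
- Multiplied form: Dose / (AUCtau × kel) = (CL/F) / kel.
- Printed ÷ multiplied = kel².

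**Step 2: units**

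- Printed: (volume/time) × (1/time) = volume/time². This is not a volume.
- Multiplied: (volume/time) ÷ (1/time) = volume. This agrees with the row's own description and with the single-dose table.

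**Step 3: illustration at 150 mg**

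The single-dose half-life range is assumed to apply to the multiple-dose predictions. The figures show how the two forms behave and are not estimates for this trial. Note that 1 µg·h/mL = 1 mg·h/L.

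- CL/F = 150 / 4486 = 0.0334 L/h, which is 0.0334 × 24 = 0.802 L/day.
- kel at 9 days = ln(2)/216 h = 0.00321 per h, or ln(2)/9 = 0.0770 per day.
- kel at 18 days = ln(2)/432 h = 0.00160 per h, or ln(2)/18 = 0.0385 per day.

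| Half-life | Multiplied form | Printed form, hours | Printed form, days |
|---|---|---|---|
| 9 days | 10.4 L | 1.07 × 10⁻⁴ L/h² | 0.0618 L/day² |
| 18 days | 20.8 L | 5.4 × 10⁻⁵ L/h² | 0.0309 L/day² |

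The multiplied form gives the same volume in either time unit. The printed form changes by 24² = 576 when hours are replaced by days. It also moves the wrong way: at fixed CL/F, doubling the half-life doubles the correct volume but halves the printed quantity.

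**Step 4: simulation**

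A one-compartment subcutaneous profile at steady state was simulated for 150 mg every 672 h. The assumed values were volume 8 L, half-life 12 days and absorption rate 0.02 per h. The multiplied form returned 8.00 L. The printed form returned 4.6 × 10⁻⁵ L/h².

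**The case against.** The strongest reply is that nothing need go wrong in practice. SAP section 2 places the SAP above the protocol's statistical text, and SAP 8.3.1 asks for conventional noncompartmental methods, which multiply AUC by kel. SAP Table 5 already departs from the protocol table on other rows: CL/F and Cav are Day 57 only rather than Days 1 and 57, and Cmin is Days 1 and 57 rather than Day 57 only. Vz/F is conditional on the data supporting it, is only summarised descriptively, and enters no model or escalation rule. A literal implementation would also produce values plainly out of line with single-dose Vz/F.

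Most of this stands, and it limits the weight of the point. A reader might infer that the reported endpoint will come out wrong. The documents do not support that; it follows only if the protocol row is programmed literally. What remains is that the SAP supplies no competing formula, so its precedence clause does not expressly replace the faulty one.

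A reader might also turn kel² into a headline understatement. With kel per hour, 1/kel² is about 97,000 at 9 days and 388,000 at 18 days. With kel per day the same half-lives give about 169 and 674. These compare quantities with different dimensions, depend on the time unit, and borrow single-dose half-lives for Day 57. None of them should be quoted as the size of the error.

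Finally, the tables were read from a PDF. The single-dose row keeps its multiplication sign, so corruption of this one operator is unlikely, but the source page should be checked.

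**Conclusion.** The multiple-dose Vz/F row in Protocol 9.3.1 is wrong as printed and contradicts the single-dose row. Followed literally, it returns a quantity that differs from Vz/F by kel² and is not a volume. This conclusion rests only on the protocol's own definitions of CL/F and kel; it needs no half-life or exposure figure.

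The reach is narrow. The error touches one descriptive secondary endpoint and does not feed AUCtau, Cmax, CL/F, half-life or Rac. The dose-proportionality plots and the bioavailability analysis in Protocol 9.3.2 and SAP 10.2.3.3 do not use Vz/F. No safety conclusion depends on it. The point should be corrected because it is definite and cheap to fix, not because it threatens the trial's findings.

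The same table describes dose-normalised Cmin as dose-normalised Cmax. The method beside it is correct (Cmin / Dose), so this is a clerical slip that changes no value.

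**What to change.** Change the Day 57 row of the multiple-dose table in Protocol 9.3.1 to Vz/F = Dose / (AUCtau × kel), and correct the description of dose-normalised Cmin at the same time. If the protocol will not be amended again, a line in SAP 8.3.1 giving the formula, and noting that it replaces the protocol row, would serve the same purpose. Either way, confirm that the analysis program uses the multiplied form. The cost is a one-operator text correction, with no change to data collection, sample size or any other analysis.

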9.3.2. Statistical Methods of PK Analysis

The serum PK parameters for RN909 (PF-06293620) will be summarized descriptively by dose and route of administration. Serum concentrations will be listed and summarized descriptively by dose, nominal PK sampling time and route of administration. Individual subject, summary profiles (mean and median plots) of the serum concentration-time data will be plotted by treatment and PK sampling time. For summary statistics and summary plots, the nominal PK sampling time will be used. For individual subject plots, the actual PK sampling time will be used, whilst the pre-dose time will be set to zero. Summary plots will be presented on both linear-linear and log-linear scales.

Dose normalized parameters for RN909 (PF-06293620) will be plotted against dose and route of administration and will include individual subject values and the geometric means for each dose. For SAD, AUC_{inf}, AUC_{last}, and C_{max} will be plotted; for MAD, AUC_τ and C_{max} (Day 1 and Day 57) and C_{min} (Day 57) will be plotted. These plots will be used to help understand the relationship between the PK parameters and dose.

Absolute bioavailability (F) will be estimated as the ratio of dose-normalized adjusted geometric means for SC and IV for AUC_{last} and AUC_{inf} . Dose-normalized natural log transformed AUC_{inf} (data permitting) and AUC_{last} will be analyzed using a mixed effect model with treatment as fixed effects and subject as a random effect using a one-way analysis of variance (ANOVA). Estimates of the adjusted mean differences (Test-Reference) and corresponding 90% confidence intervals will be obtained from the model. The adjusted mean differences and 90% confidence intervals for the differences will be exponentiated to provide estimates of the ratio of adjusted geometric means (Test/Reference) and 90% confidence intervals for the ratios. SC doses are the Test treatments, and IV is the Reference treatment.

Subjects having positive ADAs will be analyzed separately to assess the effects of ADAs on RN909 (PF-06293620) concentrations. If there is no effect on the concentration versus time profiles, then these subjects will be included in the descriptive statistics of concentrations and PK parameters.

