10.2.3. PK Analyses

10.2.3.1. Concentrations below the limit of quantification

In all data presentations (except listings), concentrations below the limit of quantification (BLQ) will be set to zero. (In listings BLQ values will be reported as “<LLQ”, where LLQ will be replaced with the value for the lower limit of quantification.)

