10.2.3.3. Pharmacokinetic parameters

Actual PK sampling times will be used in the derivation of PK parameters.

If a PK parameter cannot be derived from a subject's concentration data, the parameter will be coded as NC (ie not calculated). (Note that NC values will not be generated beyond the day that a subject discontinues.)

In summary tables, statistics will be calculated by setting NC values to missing; and statistics will not be presented for a particular treatment if more than 50% of the data are NC. For statistical analyses (ie analysis of variance), PK parameters coded as NC will also be set to missing.

If an individual subject has a known biased estimate of a PK parameter (due for example to an unexpected event such as coughing during or immediately after inhalation before all of the drug is absorbed by the body), this will be footnoted in summary tables and will not be included in the calculation of summary statistics.

To assess the pharmacokinetics of PF-06293620, PK parameters will be listed and summarized for subjects in the PK analysis set (as defined in [Section 7](#)). Missing values will be handled as detailed above.

The PK parameters to be summarized by treatment are outlined in Table 8.

Table 8. SAD and MAD Cohorts PK Parameters:

Parameter	Summary statistics
SAD Cohort	
AUC _{inf} , AUC _{last} , C _{max} , V _z /F, V _{ss} , CL/F, CL, AUC _{inf} (dn), AUC _{last} (dn), C _{max} (dn)	N, arithmetic mean, median, cv%, standard deviation, minimum, maximum, geometric mean, geometric CV%.
T _{max}	N, median, minimum, maximum.
t _{1/2}	N, arithmetic mean, median, cv%, standard deviation, minimum, maximum.
MAD Cohorts	
AUC _τ , C _{max} , C _{min} , CL/F, C _{av} , V _z /F, R _{ac} , R _{ac,Cmax} , AUC _τ (dn), C _{max} (dn), C _{min} (dn)	N, arithmetic mean, median, cv%, standard deviation, minimum, maximum, geometric mean, geometric CV%.
T _{max}	N, median, minimum, maximum.
t _{1/2}	N, arithmetic mean, median, cv%, standard deviation, minimum, maximum.

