SAD Cohorts: To assess the relationship between the PK parameters and dose, dose normalized AUC_{inf}, AUC_{last} and C_{max} will be plotted against dose (using a logarithmic scale), and will include individual subject values and the geometric means for each dose. Geometric means will have a different symbol than the individual values. The values will be dose normalized (to a 1 mg/kg dose) by dividing the individual values and raw geometric means by dose. A footnote will be added to the plots to indicate that geometric means are presented on the plot.

Absolute/Relative bioavailability will be estimated as the ratio of dose-normalized adjusted geometric means for SC and IV for AUC_{last} and AUC_{inf}.

MAD Cohorts: To assess the relationship between the PK parameters and dose, dose normalized AUC_τ and C_{max} on Days 1 and 57, and dose normalized C_{min} on Day 57, will be plotted against dose (using a logarithmic scale), and will include individual subject values and the geometric means for each dose. Geometric means will have a different symbol than the individual values. The values will be dose normalized (to a 1 mg/kg dose) by dividing the individual values and raw geometric means by dose. A footnote will be added to the plots to indicate that geometric means are presented on the plot.

Dose-normalized natural log transformed AUC (SAD): AUC_{inf} (data permitting) and AUC_{last} ; and $AUC\tau$ (MAD) will be analyzed using a mixed effect model with treatment as fixed effects and subject as a random effect using a one-way analysis of variance (ANOVA). Estimates of the adjusted mean differences (Test-Reference) and corresponding 90% confidence intervals will be obtained from the model. The adjusted mean differences and 90% confidence intervals for the differences will be exponentiated to provide estimates of the ratio of adjusted geometric means (Test/Reference) and 90% confidence intervals for the ratios. SC is the Test treatment, and the IV is the Reference treatment.

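### Exposure against dose is read only from plots, with no slope or interval, and one plotted SAD parameter (AUClast) can rise with dose under linear PK

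*Protocol*

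**What the plan says.** Protocol 9.3.2 plots dose-normalised AUCinf, AUClast and Cmax for SAD. For MAD it plots AUCtau and Cmax (Days 1 and 57) and Cmin (Day 57). Individual values and geometric means are shown, and "These plots will be used to help understand the relationship between the PK parameters and dose". SAP 10.2.3.3 gives the same plots the task "To assess the relationship between the PK parameters and dose".

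The only model for exposure is an ANOVA on log dose-normalised AUC with SC as test and IV as reference. It gives 90% intervals for bioavailability. The SAP also lists the MAD AUCtau for this model, but every final MAD cohort in SAP Table 2 is SC, so there is no IV reference there.

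Protocol 9.3.1 defines AUClast as "Area under the serum concentration-time profile from time zero to the time of the last quantifiable concentration". The MAD AUCtau covers a fixed 672 h at every dose. AUCinf is derived only if the data permit, and SAP 10.2.3.3 adds that "statistics will not be presented for a particular treatment if more than 50% of the data are NC" (NC meaning not calculated). SAP 10.2.3.1 says that "concentrations below the limit of quantification (BLQ) will be set to zero" in data presentations, but neither document states the limit.

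Protocol 1.3.2 reports that Cmax and AUCinf "increased slightly greater than dose proportionally with increasing doses up to 6 mg/kg".

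**The concern.** Characterising PK is the secondary objective, and how exposure scales with dose is part of it. Two features weaken the planned reading.

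First, a plot gives no estimate of how far exposure departs from proportionality, and no uncertainty. Readers can put different words on the same picture.

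Second, the end point of AUClast can depend on dose. A lower dose reaches the assay limit sooner, so a smaller share of its curve is counted. Dividing by dose does not correct that, and the plotted values then climb with dose although clearance is constant. AUCinf would correct it, but it may have no summary at the lowest dose.

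**Working it through.** The documents give no dose slope to reproduce, so the check has four parts.

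**1. The protocol's own AUCinf.** The geometric means in protocol Table 2 are 260, 1748 and 6606 µg·hr/mL at 0.3, 1 and 3 mg/kg; 6 mg/kg was not calculated.
- Per mg/kg: 260/0.3 = 867; 1748/1 = 1748; 6606/3 = 2202.
- Over the 10-fold dose range: 6606/260 = 25.4-fold. Exponent: ln(25.4)/ln(10) = 1.40.
- The N, n row reads 6,2; 6,5; 6,6; 6,0. Its key is not in the available text. Read as subjects with a calculable AUCinf, a least-squares line weighted by n = 2, 5, 6 has slope 1.37. With CV 45% the 90% half-width is 0.26, so the interval is about 1.11 to 1.63.

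**2. Availability of AUCinf.** If 2 of 6 at 0.3 mg/kg persists, 4/6 = 67% are NC. That exceeds 50%, so the summary for that dose is not presented.

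**3. Size of the AUClast artefact under linear PK.** Inputs:
- a one-compartment SC model with half-life 9 or 18 days and Tmax 4 or 10 days (the ends of the ranges in protocol 1.3.2);
- the SAD sampling times to Day 85;
- the linear/log trapezoid up to the last value at or above the LLOQ.

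The LLOQ is an assumption, entered as the ratio of Cmax at 0.3 mg/kg to LLOQ. The result is dose-normalised AUClast at 6 mg/kg divided by that at 0.3 mg/kg, which should be 1, as a range over the four half-life and Tmax combinations:

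| Cmax at 0.3 mg/kg ÷ LLOQ | Ratio, 6 to 0.3 mg/kg |
|---|---|
| 2 | 1.60–1.83 |
| 3 | 1.27–1.63 |
| 5 | 1.11–1.30 |
| 10 | 1.09–1.14 |
| 20 | 1.00–1.09 |
| 50 | 1.00–1.03 |

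For ratios of 2 to 10, the last quantifiable visit is Day 15 to 57 at 0.3 mg/kg and Day 43 to 85 at 6 mg/kg.

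**4. Precision of a fitted exponent.** Model: ln(parameter) = a + b ln(dose). SD on the log scale: s = sqrt(ln(1 + 0.45²)) = 0.429, using the CV of about 45% in Table 2. SE(b) = s/sqrt(Sxx), where Sxx is the sum over subjects of (ln dose − mean)².
- SAD SC, four doses, 6 each: Sxx = 6 × 5.156 = 30.94; SE = 0.429/5.562 = 0.077; t(22 df) = 1.717; half-width 0.13.
- SAD SC with 2, 5, 6, 6 contributing: SE 0.102; half-width 0.18.
- MAD, 8/16/8 at 50/75/150 mg, with the same CV assumed: Sxx = 4.99; SE = 0.429/2.235 = 0.192; t(30 df) = 1.697; half-width 0.33.

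**The case against.** The strongest reply is that the plan does not depend on AUClast. Cmax and AUCinf are plotted beside it, and the MAD plots use AUCtau over a fixed interval. SAP 10.2.3.4 also tabulates how many concentrations exceed the assay limit by dose and time, and plots profiles on a log scale. This stands. A reader might infer that artefact and true nonlinearity cannot be separated; the documents do not support that, because early truncation at low doses would show in those displays.

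A reader might also infer that the reported more-than-proportional rise is itself the artefact. It is not shown to be. The Table 2 figures are AUCinf, which is extrapolated and not cut off. The model-predicted AUCtau in protocol Table 4 rises too: 1471/75 = 19.6, 4486/150 = 29.9 and 9448/250 = 37.8 per mg. The reported half-life also lengthens with dose.

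Nor would the eye usually get the direction wrong. With a true exponent of 1.2, CV 45% and 6 per dose, the lowest and highest dose means are ordered wrongly 0.8% of the time, against 0.5% for the fitted slope. The 1 and 3 mg/kg means alone would err 19% of the time, but nobody plans to use only those. What the slope adds is a size and an interval.

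Finally, the study is exploratory, has no hypothesis tests and does not name dose proportionality as an objective. The SAP permits unplanned analyses, and the ANOVA gives intervals for SC doses against IV. All true. Those intervals compare route, however, and are not intervals on dose. An estimate without a test fits an exploratory study.

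**Conclusion.** The point holds as an improvement and not as an error in a stated analysis. The dose relationship is assessed by plots alone, and no slope or interval on dose is planned.

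The AUClast bias is certain in direction only if low-dose concentrations become unquantifiable before Day 85. Its size rests on the unstated LLOQ: about 1.1- to 1.8-fold at 2 to 10 times the LLOQ, and 0 to 9% at 20 times. It also rests on the one-compartment linear model. The possible loss of the AUCinf summary at 0.3 mg/kg rests on the interim count persisting and on reading that count as 2 of 6.

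The half-widths of 0.13 and 0.33 assume a CV of 45% and full cohorts. The SAD estimate would be informative and the MAD estimate only rough.

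**What to change.** Keep the plots. Add to protocol 9.3.2 and SAP 10.2.3.3 a descriptive power model, ln(parameter) = a + b ln(dose), reporting b with a 90% confidence interval and no test. Fit it, with dose in the units given, to:
- SAD SC: Cmax, AUCinf where calculable, and an AUC over the longest common interval quantifiable at all SC doses. Choose the interval from the counts of quantifiable samples before looking at the AUC values.
- MAD: Cmax and AUCtau, Days 1 and 57.

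State the LLOQ in the SAP, and say that the dose-proportionality reading will not rest on AUClast alone.

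The cost is one extra derived AUC and one regression per parameter, with no new samples. There are two limits. One exponent is only a summary if the relation is curved; the interim AUCinf means give local exponents of ln(1748/260)/ln(1/0.3) = 1.58 and ln(6606/1748)/ln(3) = 1.21, the first resting on apparently two subjects at 0.3 mg/kg. A short common interval is also less sensitive to dose-dependent elimination. Under the model above, 0 to Day 15 holds only 30 to 61% of total exposure. The longer 0 to 672 h interval would not be fully quantifiable at 0.3 mg/kg in three of the four scenarios if Cmax there is twice the LLOQ. The plots should therefore stay beside the estimate.
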